The target sample size is 1,462 total participants (731 per treatment group) enrolled from 27 VA medical centers. This sample size will provide 90% power to detect a 25% reduction in the hazard from all-cause mortality, and will provide ample power to identify clinically meaningful differences in treatment effect across co-morbidity levels.

Analytic Plans

The statistical analysis plans are straightforward and appropriate. The primary outcome of all-cause mortality will be analyzed as time to event and tested by the stratified log rank statistic (stratified by site and Charlson score <3 versus ≥ 3) with a type I error of 0.05 (2-sided). Patients who are lost or withdraw prior to an outcome assessment, or who do not experience an event will be right-censored at date of last contact, date withdrawn, or date of study exit. VA Vital Status File will be used to determine the vital status of all study participants who are lost to follow-up at study exit.

Budget

The total estimated study budget is \$12.5 million. The budget is based on 3 years of participant intake and minimum follow-up of 2 years, with follow-up completed centrally after completion of post-implantation clinic visit, and accounts for both the Pilot and Full-scope stages of the study.

[name], PhD
Director, WH-CSPCC

Director: Cooperative Studies Program Clinical Research Pharmacy Coordinating Center

**DEPARTMENT OF VETERANS AFFAIRS
VA Cooperative Studies Program
Clinical Research Pharmacy Coordinating Center (151-I)
[name]
[name]**

February 20, 2015

501/151-1
In Reply Refer To: CSP #95/CSP #592
File: STD_DOC

[name], PhD
Acting Chief Research and Development Officer
VA Central Office
[name]
[name]

Dear [name]:

SUBJ: CSPCRPCC Issues Letter for CSP #592 / "Efficacy and Safety of ICD Implantation in the Elderly"

There are no PCC issues related to this study. The PCC will provide safety monitoring and MedDRA coding for the duration of the study. The study does not require either an Investigational New Drug (IND) or Investigational Device Exemption (IDE) application.

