While these lifestyle modifications cannot be mandated, participant compliance with these conventions will be strongly encouraged. Per clinical trial evidence linking outcome to dose, all participants will be strongly recommended to be on maximum tolerated doses of a beta blocker and an ACE inhibitor or ARB⁷⁴ to be eligible for entry into the study. Optimal medical therapy was chosen to explicitly test the efficacy and safety of the ICD on top of guideline-driven medical care.

D. Outcome Measures and Rationale

This study is designed to compare the efficacy and safety of ICD implantation in an aged population in reducing all-cause mortality. The primary outcome is measured by survival time. The study is designed to detect 25% reduction in the hazard of all-cause mortality among participants randomized to ICD with an estimated average follow-up of 3.6 years. Key secondary analyses will be quality of life and the effect of ICD in high- versus low co-morbidity burden. Quality of life (QoL) will be measured by the Minnesota Living with Heart Failure

questionnaire, a cardiac disease-specific QoL instrument. Quality of Life will be measured at baseline, six months, twelve months, and twenty-four months.

E. Sample Size

The target sample size for CSP #592 is 1,462 total participants (731 per treatment group to achieve a total of 565 primary outcome events). This sample size will provide 90% power to detect a 25% reduction in hazard from all-cause mortality between ICD + OMT and OMT alone, and will provide ample power to identify clinically meaningful differences between treatments in longer-term safety and Quality of Life measures, as well as significance in the treatment interaction based on co-morbidity burden.

F. Data Collection and Assessments

Study participants will be assessed at baseline via in-person clinic visit and at month 1 to 4 following randomization and every 6 months thereafter via phone-based centralized follow-up; information related to the device will be collected on the day of implantation. The maximum follow-up is 5 years, the average participant follow-up across all participants (recruited in the pilot and full-scale stages) is 3.6 years. Chapter VIII provides details of the baseline assessments and procedures and Chapter 0 describes details of the follow-up schedule and procedures.

G. Alternate Design Considerations

1. Age Eligibility Criterion

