H. Justification of Stratification at Charlson Index 3

Though general health status does not appear to be associated with the rate of ICD implantation, whether there exists an interaction between co-morbid burden and treatment effect remains to be seen. Accordingly, this study will stratify on the basis disease burden, specifically participants will be stratified into “fair” and “poor” health status, on the basis of their Charlson score being lesser versus greater than/equal to 3. This threshold was established following the database review, and in consideration of the general criteria for implantation. Because those patients with the highest co-morbidity score would likely be determined to be ineligible for study (on the basis of 1-year survivability) we estimated the median Charlson score of study-eligible patients would be closer to Charlson score of 3. In this context, a classification of “fair” health status as corresponding to Charlson score of <3 is well-suited in terms of study feasibility, and would commensurate with the existing body of literature to which this study will ultimately be compared. This stratification is in addition to stratification by site.

VI. OUTCOME MEASURES

A. Primary Outcome

The primary outcome measure for this study will be death from any cause analyzed as time to event. The date of randomization will be used as the time origin. VA Vital Status File will be used to determine the vital status of all study participants who are lost to follow-up at study exit. The VA Vital Status File has been shown to be highly accurate compared to the National Death Index (NDI) ⁸³. As cause of death is not available from the VA Vital Status File, a NDI Plus database search will be performed for all participants who are found to have died through the database search in order to adjudicate the cause of death for secondary outcomes.

B. Secondary Outcomes and Exploratory Analyses

1. Quality of Life

Among the cardiac-specific quality of life (QoL) instruments, the Minnesota Living with Heart Failure questionnaire (MLHF) is considered to be among the best ⁸⁴. It has been widely validated ⁸⁵⁻⁸⁷, and it is more sensitive than the generic QoL measures in detecting clinically important changes over time in patients with heart failure ^{88,89}. The MLHF was also chosen as the QoL measure for this study because it is simple, inexpensive, short, easily understood by ill and elderly individuals, self-administered, and easy to score ⁹⁰⁻⁹⁷.

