Because the VA Vital Status File will be searched for all deaths, loss-to-follow-up for the primary endpoint is considered to be very negligible and was therefore not accounted for in the sample size calculation. Based on a 15% annual event rate in the control arm and a hazard ratio of 0.75, and the other assumptions listed above, a sample size of 1,462 (565 total primary outcome events) will be needed in order to achieve 90% power with a 2-sided Type I error rate of 0.05.

Using the target sample size of 1,462, the following scenarios were considered as sensitivity analyses:

- If the recruitment rate is less than anticipated, the study will still maintain 80% power to detect a hazard ratio of 0.75 with 1,084 participants (422 events).
- If the control group annual event rate was 3% lower than anticipated (i.e. 12% annual mortality rate) the study would still maintain 81.0% power to detect a hazard ratio of 0.75.
- If the effect size is smaller than hypothesized, the study would still maintain 80% power to detect a hazard ratio of 0.78.

3. Power for Secondary Analyses

The secondary objectives for this trial are to test the treatment interactions by co-morbidity level, and to test the change from baseline in the Minnesota Living with Heart Failure score. Neither secondary analysis will require adjustment for type I error, i.e. no “multiple testing” corrections: adjustments for multiple comparisons are required in confirmatory whenever results from multiple tests have to be combined in one final conclusion and decision; in studies with a single primary endpoint, all other endpoints are considered subsidiary and their results can only have an exploratory rather than a confirmatory interpretation – multiplicity corrections are not required¹²⁴. A sample size of 1,462 participants will yield the following power for secondary endpoints:

- Assuming equal enrollment across high- and low-burden groups, this study will reach statistical significance for an increased in therapeutic effect by 50% in the low-burden group (Charlson <3) and decrease in efficacy of 50% in the high-burden group (Charlson ≥ 3). Assuming a pooled standard deviation of 5 for change from baseline in Minnesota Living with heart failure score, the study will have 80% power to detect a 0.73 difference between groups in mean change from baseline at 12 months.

B. Interim Monitoring and Analysis

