The analysis of the primary outcome, all-cause mortality, will be analyzed as time to event and tested by the stratified log rank statistic (stratified on site and Charlson score <3 versus ≥ 3), with a type I error of 0.05 (2-sided). Cumulative survival rates will be calculated using the method of Kaplan-Meier. The treatment effect will be estimated from a stratified Cox proportional hazards model and summarized as a hazard ratio (ICD versus optimal medical therapy) with a 95% confidence interval. The assumption of proportionality will be tested by treatment by time

interaction term prior to fitting the model. The start time for all time-to-event analyses will be defined as the date of randomization and participants who do not experience an event will be right-censored at the date of last contact, date withdrawn, or date of study exit. VA Vital Status File will be used to determine the vital status of all study participants who are lost to follow-up at study exit.

3. Secondary Analyses

The overall type I error for the secondary outcomes will be of 0.05 (2-sided) without adjustment for multiple comparisons.

a) Treatment Interactions by Co-Morbidity

The primary analysis of the treatment interaction with co-morbidity will take the form of a time to event, and will be analyzed using the same methodology described for the primary outcome at a 0.05 2-sided significance level. A test of treatment interaction by Charlson score <3 versus ≥ 3 (alternative subgroups will also be explored) and by Charlson score as a continuous measure. In addition, a forest plot and treatment interaction will be examined for each type of comorbidity.

b) Quality of Life

The primary analysis of QoL will be a comparison between treatment groups of the change in the Minnesota Living with Heart Failure questionnaire scores at 12 months post-randomization relative to baseline using a two-sample t-test if the data appear sufficiently normal and a non-parametric method if the normality assumption looks like it does not hold.

4. Exploratory Analyses

a) Quality of Life

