2.2.3 Analysis of the Primary Outcome

For all the endpoints (primary, secondary, and exploratory) we will present summary information, as well as estimated result with p-value from an appropriately selected hypothesis test. The number of participants reaching the primary endpoint will be summarized in terms of total number participants as well as percent by treatment arm and treatment stratified by health stratum.

Treatment effect on the primary outcome, all-cause mortality, will be analyzed as time to event and tested by the stratified log rank statistic (stratified by Charlson score <3 versus ≥ 3), with a type I error of 0.05 (2-sided). Cumulative survival rates will be calculated using the method of Kaplan-Meier. The treatment effect will be estimated from a Cox proportional hazards model, adjusted by Charlson score and provided as a hazard ratio (ICD versus optimal standard of care) with a 95% confidence interval. The start time for all time-to-event analyses will be defined as the date of randomization and participants who do not experience an event will be right-censored at the date of last contact, date withdrawn, or date of study exit. VA Vital Status File will be used to determine the vital status of all study participants who are lost to follow-up at study exit.

Prior to Cox model fitting, the assumption of proportionality will be tested via treatment by time interaction term. If the assumptions of proportionality are not fulfilled, there will be no impact on the primary hypothesis test since we apply log-rank test on the primary

hypothesis test. We may estimate the hazard ratio by introducing interactions of treatment with function of time in the model. In addition, we will also test the treatment and Charlson stratum interaction in the Cox proportional hazards model²⁵. Breslow's approximation, which is the default in PROC PHREG in SAS, will be used to handle tied event times when ties are relatively few²⁶. If data are moderately- or heavily tied, we will use Efron's method, which gives closer results to the exact results than Breslow's approximation^{27,28}.

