2.2.6.1 Treatment Interactions by Co-Morbidity

The primary analysis of the treatment interaction with co-morbidity will take the form of a time to event, and will be analyzed using the same methodology (log-rank test) described for the primary outcome at a 0.05 2-sided significance level. The treatment effect will be summarized as a hazard ratio with 95% confidence interval. A test of treatment interaction by Charlson score <3 versus ≥ 3 (alternative subgroups) will also be performed.

In the study, the original Charlson score is a continuous variable. It is known that dichotomizing a continuous outcome into low or high values leads to a loss of information^{32,33}. Therefore, to keep the statistical power of the analysis, the testing of interaction will also be conducted by treating Charlson score as a continuous measure, via the Cox model, cf. the log-rank test for dichotomous formulation. The results from the above two methods will be compared, and they should be similar. In addition, a forest plot and treatment effects will be examined for each type of co-morbidity.

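### Power for the treatment-by-co-morbidity interaction is called ample, but the plan's only scenario gives about 52% for the Charlson <3 versus ≥3 test

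*Combined protocol and SAP*

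**What the plan says.** The Coordinating Center director's letter (Sample Size) says that 1,462 participants "will provide ample power to identify clinically meaningful differences in treatment effect across co-morbidity levels". Protocol section III.E makes the same claim of ample power for longer-term safety and quality of life, "as well as significance in the treatment interaction based on co-morbidity burden".

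The only support is in section XV.A.3, in a list presented as the power of the secondary analyses. The entry reads: "Assuming equal enrollment across high- and low-burden groups, this study will reach statistical significance for an increased in therapeutic effect by 50" per cent among participants with Charlson <3, paired with efficacy 50% lower at Charlson ≥3. No power percentage follows. The quality-of-life statement beside it does give one (80%).

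On the mix of participants, section V.H expects the highest scores to be screened out by the one-year survival requirement, so that "we estimated the median Charlson score of study-eligible patients would be closer to Charlson score of 3".

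On the test, protocol section XV.C.3.a says the interaction "will be analyzed using the same methodology described for the primary outcome at a 0.05 2-sided significance level". SAP 2.2.6.1 narrows this to "will be analyzed using the same methodology (log-rank test) described for the primary outcome at a 0.05 2-sided significance level". The same SAP section later contrasts a Cox model for continuous Charlson with the log-rank test for the two-group version. SAP 2.2.3 separately states that "we will also test the treatment and Charlson stratum interaction in the Cox proportional hazards model".

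**The concern.** An interaction test is far less powerful than the main-effect test on the same events, so ample power in a trial sized for the main effect needs a calculation behind it. The plan shows none. Its statement that the scenario will reach significance looks like a smallest-significant-difference calculation: if the observed effects equal the assumed ones, p falls just below 0.05. That condition corresponds to roughly 50% power.

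The question matters to the trial. SAP 1.1.2 describes efficacy under high versus low co-morbidity burden as a particularly important secondary objective, and protocol section III.G.3 gives direct testing of this interaction as the reason for stratifying on Charlson score. A reader who trusts the power claim could take a non-significant interaction as evidence that benefit does not vary with co-morbidity.

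The SAP wording adds a second problem. The primary log-rank is stratified by Charlson score. It tests whether there is a treatment effect common to the strata, not whether the effect differs between them.

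**Working it through.** **Inputs from the plan**
- 565 deaths, N = 1,462, 90% power for the primary test (XV.A.2)
- Overall HR 0.75, 1:1 allocation, 15% annual control mortality (XV.A.2)
- Effect 50% larger and 50% smaller in two equally enrolled strata (XV.A.3)
- Two-sided 0.05 for the interaction (XV.C.3.a, SAP 2.2.6.1)

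Assumption: each stratum's share of deaths equals its share of participants.

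**The plan's own figure.** A Markov log-rank calculation with control hazard −ln(0.85), the planned drop-in and drop-out, staggered entry and 1% annual loss gives 564.6 deaths and 90.0% power. The primary design therefore reproduces. There is no printed interaction power to reproduce.

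**Scenario hazard ratios**
- Low burden: 25% × 1.5 = 37.5% reduction, HR 0.625
- High burden: 25% × 0.5 = 12.5% reduction, HR 0.875
- Ratio of HRs: 0.875/0.625 = 1.40; ln(1.40) = 0.3365

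**Power at an equal split**
- SE of the log ratio of HRs = √(4/d_low + 4/d_high) = √(16/565) = 0.1683
- z = 0.3365/0.1683 = 2.00 (p = 0.046 if the observed effects equal the assumed ones)
- Power = Φ(2.00 − 1.96) = 51.6%

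A Cox simulation of 4,000 trials (731 per stratum, no crossover, about 575 deaths) gives 52.2% power. Type I error is 5.0% with HR 0.75 in both strata.

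**What 80% power would take**
- Deaths = 16 × (1.96 + 0.8416)² / 0.3365² = about 1,109. This is 1,109/1,462 = 76% of all participants, against projected mortality of 42.0% and 34.1%.
- Ratio of HRs detectable with 565 deaths = exp(2.8016 × 0.1683) = 1.60

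**Sensitivity to the split.** Shares are from Table 7 (section V.E), with and without scores of 5 or more. Dropping those scores is a reading of V.H; the plan names no cut-off.

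| Low-burden share | SE | z | Power |
|---|---|---|---|
| 50% (plan) | 0.1683 | 2.00 | 51.6% |
| 827/2,004 = 41.3% (no ICD, scores 1–4) | 0.1709 | 1.97 | 50.4% |
| 281/813 = 34.6% (ICD, scores 1–4) | 0.1769 | 1.90 | 47.7% |
| 827/4,070 = 20.3% (no ICD, all) | 0.2091 | 1.61 | 36.3% |
| 281/1,633 = 17.2% (ICD, all) | 0.2229 | 1.51 | 32.6% |

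The detectable ratio at 80% power is 1.61 and 1.64 for the 41.3% and 34.6% shares, and 1.80 at a 20/80 split.

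**Other readings, equal enrolment**
- ±50% applied to the log HR: 0.75^1.5 = 0.650 and 0.75^0.5 = 0.866; ln ratio 0.2877, z = 1.71, power 40.1%
- Planned crossover included: diluted HRs 0.641 and 0.881, z = 1.90, power 47.5%
- Crossover plus control hazards 20% lower and 20% higher in the low- and high-burden strata (illustrative): z = 1.85, power 45.7%

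**The case against.** The plan prints no wrong number. It never states a power for the interaction, 565 is the event target for the primary test, and the sentence in XV.A.3 is literally true as a statement about the smallest difference that would be significant. The 80% benchmark is this review's choice. Both documents say that secondary results can only be exploratory, and no stopping or sample-size decision depends on this test. The plan also includes a continuous-Charlson interaction, added because dichotomizing loses information. And SAP 2.2.6.1 does add "A test of treatment interaction by Charlson score <3 versus" ≥3, so the log-rank phrase may be loose drafting.

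Much of this is fair as to weight. The defect is an adequacy claim that the design does not support, not a misprinted figure. The power of the continuous test cannot be computed from the documents, so the 52% applies only to the dichotomous test. The equal-share assumption is also doubtful, since section V.E links higher scores to much higher mortality.

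None of it makes the power ample. The XV.A.3 sentence is presented as the power statement, 80% is the level used for the item next to it, and the questionable assumptions favour the plan. Exploratory status excuses the absence of multiplicity control; it does not change the power. On the test, SAP 2.2.6.1 names the log-rank for the dichotomous version twice, so the text needs correcting even if the intent was sound.

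**Conclusion.** The concern holds. For the Charlson <3 versus ≥3 interaction, the plan's own scenario has about 52% power with 565 deaths split equally. A true difference of that size would be missed by this test about half the time. The figure assumes deaths divide as enrolment does, no dilution by crossover, and the ±50% applied to the 25% hazard reduction. Relaxing any of these lowers power, to 40–50% under most of the readings tried and to 33–36% if enrolment mirrors the full Table 7 pool. No two-sided variant examined comes near 80%.

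The SAP also gives two different tests for the dichotomous interaction, and only the Cox treatment-by-stratum term in SAP 2.2.3 answers the question. The primary analysis is unaffected. The point should be corrected because it governs how a null interaction will be read.

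**What to change.** In protocol sections III.E and XV.A.3, remove the claim of ample power for the interaction and the statement that significance will be reached. Suitable text for XV.A.3:

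> With 565 deaths and equal enrolment, power for the Charlson <3 versus ≥3 interaction test is about 50% if the hazard ratios are 0.625 and 0.875. The ratio of hazard ratios detectable with 80% power is about 1.6. If enrolment follows the full Table 7 distribution, power is about 36% and the detectable ratio about 1.8.

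A note that power for the continuous-Charlson test has not been calculated would be useful. Amending the director's letter is optional, as it is a dated submission document.

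In SAP 2.2.6.1, replace the log-rank wording for the dichotomous interaction with a cross-reference to the Cox treatment-by-Charlson-stratum term in SAP 2.2.3, and report the ratio of hazard ratios with its 95% confidence interval.

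The cost is a few sentences in the protocol and SAP and a less favourable stated power. No additional participants, data or analyses are needed.

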The MLHF questionnaire is designed to specifically assess the impact of heart failure on QoL. It consists of 21 questions that measure the effect of symptoms specifically related to heart failure and its treatment in adults ^{98,99}. The response to each question is scored on a 6-point Likert scale

(0-5). There are two subscales to MLHF: physical and emotional. The effect size outcomes of several studies employing QoL are summarized in the following table.

Table 9: Effect sizes reported using Minnesota Living with Heart Failure survey. MLHF on 105-point scale, including their calculated significance. Original references listed.		
Effect Size	Interpretation	Source
1	Not significant	Rector, 1992 ⁹⁷
1.6	Not significant (P=0.33)	Kasper, 2002 ⁹⁶
4	P<0.001	Rector, 1992 ⁹⁷
5	Not significant	Owen, 2000 ⁹⁴
6.6	P=0.0006	Kasper, 2002 ⁹⁶
6.7	Not significant (P=0.41)	Curiati, 2005 ⁹⁹
9.6	P=0.01	Kasper, 2002 ⁹⁶
11.6	P=0.02	Curiati, 2005 ⁹⁹

A disease-specific instrument was chosen in favor of a broader (“generic”) QoL assessment for the reason that questionnaires with greater emphasis on ICD-specific and arrhythmia-specific measures may be more sensitive to changes in outcome, and would be more impactful in addressing ICD as a treatment choice for life threatening arrhythmias ¹⁰⁰. The Minnesota Living with Heart Failure is designed to capture both physical and emotional (anxiety or distress) dimensions of patient well-being and is considered an effective and efficient instrument ¹⁰¹. The MLHF is a proprietary instrument; its use requires procurement of a one-time licensing contract through the University of Minnesota.

2. Co-morbidity Burden

One of the primary reasons for doing a study like CSP #592 is to determine whether there are differential risk-benefit issues in the elderly: in patients with declined health status, the

likelihood of surviving long enough to derive benefit from device implantation is decreased. This study will test whether poor general health status shifts the risk-benefit profile. In this way, the Charlson Co-Morbidity Index is the most practical tool for incorporation into CSP #592, as it is an extensively validated method of measuring the prognostic impact of co-morbid disease^{80,102}.

3. Sudden Cardiac Death

Sudden cardiac death will include deaths that occur unexpectedly that is not preceded by an acute myocardial infarction. SCD will include the following events¹⁰³:

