	NYHA Class III	0.37 (0.15 – 0.90)
Bardy 2005 ²⁹	All patients	0.77 (0.62 – 0.96)
	Ischemic Chronic Heart Failure	0.79 (0.60 – 1.04)
	Non-Ischemic Chronic Heart Failure	0.73 (0.50 – 1.07)
	NYHA Class II	0.54 (0.40 – 0.74)
	NYHA Class III	1.16 (0.84 – 1.61)
Chan 2009 ⁵³	>75 years	0.59 (0.39 – 0.90)
Santangeli 2010 ⁶²	>60-65 years (meta-analysis)	0.75 (0.61 – 0.91)
Kong 2011 ⁷⁰	>75 years (meta-analysis)	0.73 (0.51 – 0.97)

The hazard ratio for effect of ICD therapy on all-cause mortality varies widely, primarily because of the differences in the populations analyzed in the various clinical trials. For this reason, it is a challenge to identify specific clinical trials on which to base our effect size assumption. However, two meta-analyses have been published that assess the impact of ICD on the elderly. In the assessment of the MADIT-II, DEFINITE, DINAMIT, SCD-HeFT and IRIS studies, a Hazard Ratio of 0.75 (95% CI 0.61 to 0.91) was found⁶²; and in a separate analysis of MADIT-I, MUSTT, MADIT-II, DEFINITE, and SCD-HeFT, a Hazard Ratio of 0.73 (95% CI

0.51 to 0.97) was found ⁷⁰. These Hazard Ratios are similar, and based on a sufficiently broad literature basis that they are the best point estimates of expectation for CSP #592. This study will adopt the more conservative of the two estimates, i.e. Hazard Ratio of 0.75.

2. Projected Sample Size

The following assumptions were used for the sample size calculation:

- Two-sided Type I error of 0.05
- Pilot stage with uniform recruitment over 1 year, with uniform follow-up of 5 years for all participants; 17 participants per site at 5 sites, i.e. $17 \times 5 = 85$ patient follow-up years
- Full-scale stage with uniform recruitment over 3 years (minimum follow-up = 2 years, maximum follow-up = 5 years, median follow-up = 3.5 years)
- Annual event rate of 15% in the control arm
- Hazard ratio of 0.75 (relative risk reduction = 23.5%)
- Allocation ratio of 1:1 for the treatment groups
- Annual drop in rate of 2.5% from the control group to the ICD group
- Drop-out rate of 1% from the ICD group to the control group in year 1 only.
- Annual loss-to-follow-up of 1%

Annual Event Rate in the Control Arm	Hazard Ratio		
	0.70	0.75	0.80
12%	1,177	1,771	2,881
15%	971	1,462	2,384
18%	834	1,258	2,057

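### The 0.73-point detectable quality-of-life difference rests on an unsourced SD of 5, hard to reconcile with Table 9, and on every participant being assessed at 12 months

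*Combined protocol and SAP*

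**What the plan says.** Protocol XV.A.3 (Power for Secondary Analyses) opens its list with "A sample size of 1,462 participants will yield the following power for secondary endpoints". For quality of life it continues "Assuming a pooled standard deviation of 5 for change from baseline in Minnesota Living with heart failure score", and concludes that "the study will have 80% power to detect a 0.73 difference between groups in mean change from baseline at 12 months". No reference or data source is attached to the SD, and no other section gives one.

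Protocol III.E gives the arm size ("731 per treatment group to achieve a total of 565 primary outcome events") and states in general terms that the sample provides "ample power to identify clinically meaningful differences between treatments in longer-term safety and Quality of Life measures".

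The test is a two-sample t-test on the change from baseline to 12 months, with a non-parametric fallback (Protocol XV.C.3.b; SAP 2.2.6.2). On the error rate, Protocol XV.C.3 says: "The overall type I error for the secondary outcomes will be of 0.05 (2-sided) without adjustment for multiple comparisons". SAP 2.2.6.2 gives the score range as 0 to 105.

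Protocol VI.B.1, Table 9 (repeated as Table 1 in SAP 1.3.2.1) lists eight MLHF effects from earlier studies, each with a significance statement and a source. The 6.7-point row is marked "Not significant (P=0.41". The table has no SDs, standard errors or sample sizes, and does not say what was compared.

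**The concern.** Quality of life is one of two secondary objectives, and 0.73 points is the only number behind its power claim. The detectable difference is proportional to the SD, so the claim is only as good as the SD of 5. An effect and its P value together imply a standard error, which allows Table 9 to be checked against that SD even though it reports no SDs. The figure also uses all 1,462 participants, while Protocol XV.A.2 expects 15% control-arm mortality per year, and someone who has died before month 12 has no 12-month score.

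If the true SD is larger, the plan overstates the precision of this endpoint. A reader relying on 0.73 could take a null result as excluding effects that the trial could not reliably detect.

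**Working it through.** **Inputs.** SD 5, 80% power and N = 1,462 (Protocol XV.A.3); 731 per arm (III.E); two-sided alpha 0.05 (XV.C.3); control mortality 15% per year, hazard ratio 0.75 and annual loss 1% (XV.A.2); Table 9 effects and P values (VI.B.1).

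**1. Reproducing the stated figure.** Detectable difference = (1.960 + 0.8416) × SD × √(2/n) = 2.8016 × 5 × √(2/731) = 0.733. This matches 0.73. One-sided alpha would give 0.65 and 90% power 0.85, so the two-sided, 80% version was used.

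**2. Setting SD 5 against Table 9.** Suppose each study had SD 5 and compared two equal arms of n. Then t = effect / (5 × √(2/n)) on 2n − 2 degrees of freedom.

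- 6.7 points, P=0.41: with n = 2, t = 6.7/5 = 1.34 on 2 df, P = 0.31. Larger n makes P smaller (0.18 at n = 3, 0.11 at n = 4). As a paired change with 2 patients, P is also 0.31. So P=0.41 cannot arise with two or more per arm, or as a paired change.
- 11.6 points, P=0.02: n = 3 gives P = 0.047 and n = 4 gives 0.017, so about 4 per arm.
- 9.6 points, P=0.01: n = 5 gives P = 0.016 and n = 6 gives 0.008, so 5 to 6 per arm.
- 6.6 points, P=0.0006, and 1.6 points, P=0.33: each falls between 15 and 20 per arm.
- 4 points, P<0.001: compatible with SD 5 at about 34 or more per arm (normal approximation).

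One row conflicts with SD 5, two fit it only in very small studies, and the rest can fit it.

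**3. Participants evaluable at 12 months.** Assume that anyone who dies or is lost before month 12 contributes no change score, and that no other questionnaires are missing.

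- OMT: 731 × 0.85 × 0.99 = 615.
- ICD: the 12-month survival is 0.85^0.75 = 0.885, and 731 × 0.885 × 0.99 = 641.

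Then √(1/615 + 1/641) = 0.0564, against √(2/731) = 0.0523. At SD 5 the detectable difference is 2.8016 × 5 × 0.0564 = 0.79.

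**4. Detectable difference (80% power) over a range of assumed SDs.**

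| Assumed SD | 731 per arm | 615 and 641 | Power for 0.73 points (731 per arm) |
|---|---|---|---|
| 5 | 0.73 | 0.79 | 80% |
| 10 | 1.47 | 1.58 | 29% |
| 15 | 2.20 | 2.37 | 15% |
| 20 | 2.93 | 3.16 | 10% |
| 25 | 3.66 | 3.95 | 8% |

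The SDs above 5 are assumptions; the documents give none.

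**5. Does the III.E statement survive?** The documents name no clinically meaningful MLHF difference. Take 4 points, the smallest effect that Table 9 reports as significant. At SD 25 with 731 per arm, power is 86%. With 615 and 641, the standard error is 25 × 0.0564 = 1.41, 4/1.41 = 2.83, and power is Φ(2.83 − 1.96), about 81%. At smaller SDs it is higher.

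**The case against.** The strongest reply is that nothing has been miscalculated. The protocol labels SD 5 as an assumption and derives 0.73 from it correctly. That stands: the dispute is over the inputs.

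A reader might go further and infer that Table 9 rules out SD 5, or that the true detectable difference is several times 0.73. The documents support neither. Table 9 does not say whether its rows are between-group or within-group comparisons, or use change scores or follow-up scores. A standard error from raw follow-up scores would not fix the SD of change. Only one row of eight conflicts with SD 5 on a t-test, and it describes another study's patients. The multiple is simply the true SD divided by 5: twofold at SD 10, threefold only at SD 15. Choosing among these needs information that the documents do not contain.

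It is also fair to say that little depends on the figure. Quality of life does not set the sample size, XV.A.3 gives non-primary endpoints only an exploratory interpretation, SAP 2.1 does not repeat SD 5 or 0.73, and the final report will show observed SDs (SAP Table 26). This limits the consequence, but does not supply a source for the SD or restore the participants expected to have died by month 12.

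**Conclusion.** The point holds in a limited form. The claim of 80% power for 0.73 points depends entirely on an unsourced SD that is hard to reconcile with the protocol's own table, and on complete 12-month assessment that its own mortality assumption contradicts.

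The attrition part follows from stated design assumptions and is small: 0.73 becomes 0.79. Questionnaires missing for other reasons would raise it further. The XV.A.2 argument that loss to follow-up is negligible relies on the VA Vital Status File, which supplies deaths but not MLHF scores.

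The SD part could matter more, but its size is unknown. Over an assumed range of 10 to 25, with expected survivors, the detectable difference runs from about 1.6 to 4.0 points.

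A reader might also infer that III.E overstates power for quality of life. That does not follow: III.E refers to clinically meaningful differences, not to 0.73 points, and power for 4 points stays at about 81% or more up to SD 25. The 4-point benchmark is itself an assumption. The fault is a misstated precision for one secondary endpoint; it does not make the endpoint unworkable.

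**What to change.** In Protocol XV.A.3, replace the single 0.73-point figure in one of two ways:

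- Give an SD of 12-month MLHF change with its source, either the MLHF trials already cited or Pilot participants pooled across arms and blinded to assignment, and recompute.
- If no sourced SD is available, state the detectable difference over a declared range of SDs, using the participants expected to be alive and followed at 12 months: about 1.6, 2.4, 3.2 and 4.0 points for SD 10, 15, 20 and 25. The values with 731 per arm (1.5, 2.2, 2.9 and 3.7) can be shown beside them as the no-attrition case.

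Either way, state the number assumed evaluable at 12 months. III.E needs no change. The cost is a few lines of text; enrolment, data collection and the planned analysis are unaffected.
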